### **15.2. Retention/Inspection of Records**

The investigator must maintain adequate and accurate records to enable the conduct of the study to be fully documented and the study data to be subsequently verified.

Records of drug receipt and disposition, electronic file of CRFs, source documents, reports of this investigation and other study documentation must be maintained by the investigator for a period of at least two years following the date on which the investigational drug is approved by FDA or other applicable regulatory agency for marketing for the purposes that were the subject of the clinical investigations. If no application is to be filed, records must be retained until two years following the date that the study is discontinued and the FDA or other applicable regulatory agency is notified. If the application is not approved by the FDA or other applicable regulatory agency for such indication, records must be retained for two years after notification by Galera Therapeutics, Inc. of the FDA or other applicable regulatory agency decision. The records must be available for copying and inspection if requested by regulatory authorities.

Galera Therapeutics, Inc. should be notified in writing at least 30 days prior to the disposal or transfer to another location or party of any study records related to this protocol.

## APPENDIX 1. SCHEDULE OF ASSESSMENTS

Assessments	Screening/ Baseline	In hospital							After discharge from ICU
		Day 1	Day 2	Day 3	Day 4	Day 5	Day 6	Day 7	
Informed consent	X								
Inclusion/exclusion criteria	X								
Age/Medical history 	X								
Predicted Body Weight 	X								
Supplemental oxygen/ventilation status and parameters 	X	X	X	X	X	X	X	X	
Blood pressure/MAP/vasopressor use 	X	X	X	X	X	X	X	X	X
Serum or urine pregnancy test	X								
12-lead ECG	X								
Concomitant medications	X	X	X	X	X	X	X	X	X
Adverse Events	X	X	X	X	X	X	X	X	X 
SaO 2 or PaO 2 /FiO 2 ratio 		X	X	X	X	X	X	X	X
SOFA score 	X	X	X	X	X	X	X	X	
Apache IV score 	X								
Daily Fluid Balance 	X	X	X	X	X	X	X		
Hematology, serum chemistry 	X	X	X	X	X	X	X	X 	X 
GC4419/placebo administration 		X	X	X	X	X	X		
Blood for cytokines 	X	X					X	X 	
Viral load testing 	X 	X					X	X 	
Pharmacokinetic blood testing 		X		X					

 Include comorbid conditions hypertension, diabetes, coronary artery disease, hyperlipidemia, asthma, other notable pre-existing conditions

 Predicted body weight: males—PBW in kg =  $50 + 2.3 \times (\text{height in inches} - 60)$ . Females— $45.5 + 2.3 \times (\text{height in inches} - 60)$

 Record maximum support needed, once per 24 hour period: ON/OFF mechanical ventilation; high-flow O2, mask, non-rebreather mask, mechanical ventilation for each 24-hour period; also record the following daily before 10 am (but at least 30 minutes after any sedation vacation): tidal volume, minute ventilation, PEEP, peak inspiratory pressure, plateau pressure, prone positioning yes/no, hours per day of prone positioning. Lung compliance to be calculated from clinical data for exploratory purposes.

 Once during screening, then q12 hours and also before each GC4419/placebo infusion, every 30 minutes during each GC4419/placebo infusion, at end of each GC4419/placebo infusion, and 1, 2, and 4 hours post GC4419/placebo

 Record vasopressor requirements once at screening and q12 hours while on vasopressors; record specific vasopressor and dose in mcg/minute; not applicable post discharge

 Record worst value once a day assessed 8am-6pm

 <https://intensivecarenetwork.com/Calculators/Files/Apache4.html>. Record worst value in past 24 hours at baseline visit only.

 Record highest value during any 24-hour period

 Performed locally. CBC with differential and platelets; sodium, potassium, chloride, CO2, BUN, creatinine, total protein/albumin, AST/ALT, and total bilirubin. Include direct bilirubin, triglycerides, C-reactive protein, and troponin at baseline only unless clinically indicated. If baseline troponin is above ULN, the highest post-baseline value during hospitalization and the value closest to date of discharged will also be collected. Record Worst Value for Any Day When Multiple Labs are Drawn.

 Administer 90 mg IV over 180 minutes, Q 12 hours (+/- 2 hours) for 7 days. It is acceptable for the timing of the first 2 doses to be modified in order to accommodate subsequent dosing on a Q12 hour schedule that meets institution's standard of care procedures. *Study drug infusions should not begin if the subject's mean arterial pressure (MAP) is less than 65 mmHg.*

 Collected once during screening/baseline, at Day 7 and Day 14 (while in the hospital); blood sample to be stored on site for analysis by central lab at end of study

 IL-1 beta, IL-6, TNF-alpha, IL-10

 Screening sample to be performed by local lab with a duplicate sample collected for central lab analysis. Subsequent samples collected at Day 7 and Day 14 (while in the hospital) for central lab analysis. Nasopharyngeal sample required unless subject is intubated, in which case pulmonary secretion collected.

 If viral load test has been performed within 7 days of baseline, no repeat is necessary at baseline

 Collected pre and post first infusion on Day 1 and Day 3 for central lab analysis

 Adverse Events will be assessed weekly after hospital discharge, for a total of 6 weeks from Day 1 and encompassing at least 30 days after end of GC4419/placebo dosing. Post-treatment AE assessments may be done on an outpatient basis for subjects who are discharged from the hospital.

 As Clinically Indicated, Record Worst Value for Any Day When Multiple Labs are Drawn.

 If subjects are not able to come into the hospital or clinic for an in-person visit, it is acceptable for a virtual visit or phone call to take place.

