### **10.2.1. Screening Phase**

The following screening observations and procedures will be completed prior to Day 1:

- Obtain a signed IRB/IEC/REB-approved informed consent
- Confirm patient eligibility by reviewing inclusion/exclusion criteria
- Obtain medical history including comorbid conditions hypertension, diabetes, coronary artery disease, hyperlipidemia, asthma, other notable pre-existing conditions
- Record predicted body weight
- Record supplemental oxygen/ ventilation status and parameters
- Blood Pressure/MAP/vasopressor use
- Collect sample for laboratory assessments per Schedule of Assessments
- 12-lead ECG
- Review of concomitant medications
- Record SOFA and Apache IV score
- Record previous day's Daily Fluid Balance, if available

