### **11.2. Sample Size**

For this group with critical disease, the null hypothesis is that 50% of subjects will survive for 28 days. The alternative hypothesis is that at least 90% of subjects receiving GC4419 will survive for 28 days compared with the control survival of 50%. A sample size of 50 subjects, 25 in each group, is expected to provide approximately 80% power to detect this difference with a two-sided alpha of 0.05.

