### **11.5.2. Secondary Efficacy Endpoints**

- safety of avasopasem
- frequency of successful ventilator weaning
- days alive and intensive care-free
- days alive and ventilator-free
- days alive with minimum  $\text{PaO}_2/\text{FiO}_2 \geq 300\text{mmHg}$
- days alive and without vasopressor/catecholamine support
- incidence of mean arterial pressure  $< 65 \text{ mmHg}$  on optimized vasopressor therapy
- days alive with a SOFA score of 6 or less
- percentage of subjects with an increase in mean arterial pressure of 10 mm Hg or more at the end of more than one infusion of GC4419

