### **11.7.2. Secondary and Exploratory Analyses**

Secondary and exploratory endpoints will be analyzed descriptively, and results tabulated. As appropriate, percentages and 95% confidence intervals will be calculated.

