## APPENDIX 2. SEQUENTIAL ORGAN FAILURE ASSESSMENT

A clinical scoring system, SOFA (Sequential Organ Failure Assessment), is used to assess a patient's mortality risk.

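### Two secondary day-count endpoints depend on the subject's state at entry, and the plan does not pre-specify adjustment for the baseline SOFA and vasopressor status it already records

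*Combined protocol and SAP*

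**What the plan says.** Section 11.5.2 lists nine secondary endpoints. Two are day counts defined by crossing a threshold: "days alive with a SOFA score of 6 or less" and "days alive and without vasopressor/catecholamine support".

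Sections 7.1 and 7.2 require respiratory failure and intensive care. Neither sets a SOFA or vasopressor limit.

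The starting state is collected for everyone. Section 10.2.1 has sites "Record SOFA and Apache IV score", and footnote 5 of Appendix 1 has them "Record vasopressor requirements once at screening and q12 hours while on vasopressors". Appendix 2 says that SOFA "is used to assess a patient's mortality risk", so the protocol itself treats the score as prognostic.

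For the analysis, Section 11.7.2 says: "Secondary and exploratory endpoints will be analyzed descriptively, and results tabulated". It adds percentages and 95% confidence intervals where appropriate, and names no baseline covariate. Section 11.3 stratifies randomization by age only. Section 11.7.1 allows covariates to be examined if a chance imbalance appears. That clause is optional, names no factor and sits under the primary mortality analysis. Section 11.1 defers technical detail to a separate statistical analysis plan, whose text is not in the document supplied.

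**The concern.** A subject who enters with SOFA at or below 6, or off vasopressors, accrues favourable days from the start unless they worsen. A subject who enters on the other side must first recover. The starting state is therefore likely to predict both counts.

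With 25 per arm and no stratification on these factors, the arms can differ noticeably by chance in how many subjects start on the favourable side. An unadjusted comparison carries that difference into the estimate. The information needed to remove it is already on the case report form, and the plan does not say it will be used for these endpoints. Section 4.3 says later trials may be considered on the basis of initial results from this one, so a difference of a day or two in these counts may be read with some interest.

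**Working it through.** **1. The plan's own figure.** Section 11.2 states "A sample size of 50 subjects, 25 in each group, is expected to provide approximately 80% power" for 28-day survival of 50% versus 90%, "with a two-sided alpha of 0.05". Pooled proportion (0.5 + 0.9)/2 = 0.7, difference 0.4:

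- n = [1.96·√(2·0.7·0.3) + 0.842·√(0.25 + 0.09)]² / 0.4² = 19.4 per arm.
- With continuity correction: (19.4/4)·[1 + √(1 + 4/(19.4·0.4))]² = 24.1, so 25 per arm.
- Continuity-corrected power at 25 per arm is 81.8%; Fisher's exact test gives 83.3%.

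The figure reproduces. It concerns mortality only and is not in question; it supplies the 25 per arm used below. No figure is given for the two day counts.

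**2. Can subjects enter on either side?** From the Appendix 2 scale:

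- Non-invasive ventilation, awake, PaO2/FiO2 below 100, no other organ affected: 4 points. Creatinine 1.2 to 1.9 adds 1. Bilirubin of 1.2 adds 1, and meets the limit of 1.5 × ULN if the ULN is at least 0.8 mg/dL (assumed; no ULN is given). Total 6, favourable side.
- PaO2/FiO2 below 200 (3 points) with a coma score below 6 (4 points): total 7, unfavourable side.

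Both are possible. The documents do not say how common each is.

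**3. Chance of a gap of 5 or more subjects (20 points) between arms of 25.** The share starting favourably is assumed.

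| Share | Independent binomial arms | Fixed total, split at random (hypergeometric) |
|---|---|---|
| 50% | 20% | 26% (25 of 50) |
| 30% or 70% | 16% | 22% (15 or 35 of 50) |

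The hypergeometric figures are for odd totals. With an even total the gap must be even, so it has to reach 6, and the chance is 11% to 16% for totals next to those shown. At a share of 10% to 20%, the binomial chance falls to 3% to 11%. A gap of 7 or more (28 points) at a 50% share has a chance of 6.5% (binomial) or 9% (25 of 50).

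**4. Size of the effect.** Assumed, none from the documents: share p = 0.5; mean day counts differ by D = 5 to 12 days between starting states; within-state SD s = 9 to 11 days.

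- Total SD = √(s² + p(1−p)D²)
- Variance explained = p(1−p)D² / total SD²
- Unadjusted SE = total SD·√(2/25)
- Adjusted SE ≈ s·√(2/25)·√(1 + 1/47)
- Shift from a 20-point gap = 0.20·D

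| s | D | Variance explained | Unadjusted SE | Shift (days) | Shift / SE | Adjusted SE |
|---|---|---|---|---|---|---|
| 9 | 5 | 7% | 2.64 | 1.0 | 0.38 | 2.57 |
| 9 | 12 | 31% | 3.06 | 2.4 | 0.78 | 2.57 |
| 11 | 5 | 5% | 3.19 | 1.0 | 0.31 | 3.14 |
| 11 | 12 | 23% | 3.54 | 2.4 | 0.68 | 3.14 |

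Adjustment narrows the 95% interval by about 1% (6.25 to 6.16 days half-width) to 16% (6.00 to 5.04). At a share of 10% to 20%, the variance explained is 2% to 22% over the same D and s, and the narrowing runs from nothing to 11%.

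**5. Given a realised gap.** Conditional coverage of the unadjusted interval is Φ[(1.96·SE − shift)/c] − Φ[(−1.96·SE − shift)/c], with c = s·√(2/25). Over the four rows it is 92% to 94% at a 20-point gap and 85% to 93% at a 28-point gap, against 95% nominal.

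**The case against.** The strongest case against acting has four parts.

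- **Randomization already deals with it.** Chance imbalance adds variance and no bias on average, and an unadjusted 95% interval allows for it over repeated trials. This stands. What remains is lost precision, and under-coverage in a trial where a large gap has occurred.
- **Nothing is tested.** These are two of nine secondary endpoints in a pilot, reported descriptively, with no error rate or decision rule attached. This stands and sets the severity.
- **The inputs are assumed.** The share, the gap in days and the SD are not in the documents. Many subjects will be intubated, and sedation may worsen the coma component, so few might start at or below 6. The chance and the gain then shrink as shown above. This stands; the upper ends of the ranges are not expected values.
- **The plan may already cover it.** The Section 11.7.1 clause does not: it is optional, triggered by a seen imbalance, unnamed, and written for mortality. The separate statistical analysis plan could not be checked. If it names these covariates for these endpoints, the point closes.

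A reader might infer two stronger things. One is that baseline imbalance could swamp the treatment contrast. The documents give no effect size or SD to support that, and under the assumed inputs the shift from a 20-point gap stays below one standard error. The other is that, for a subject starting on the favourable side, the count is little more than days alive. That is wrong: such a subject can go on to develop shock or organ failure, which Section 4.1.1 describes in this population and Section 7.3 says the drug may attenuate. Staying on the favourable side is part of what these endpoints measure.

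**Conclusion.** The point holds as a low-severity improvement that costs nothing in data or patients. Entry is open on both sides of both thresholds, the starting state is recorded, and the protocol text specifies no use of it for these two endpoints.

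With 30% to 70% starting on the favourable side, a gap of 20 points or more has roughly a one in five chance (16% to 26% across the binomial and odd-total calculations), and less if the share is more extreme. With a 50% share, 5 to 12 days between starting states and a within-state SD of 9 to 11 days, a 20-point gap shifts the arm difference by 1.0 to 2.4 days. That is 0.3 to 0.8 of a standard error, and the starting state accounts for 5% to 31% of the variance. The consequence is avoidable imprecision and a possible conditional shift in the trial as realised. It is not an error in the plan, not average bias, and has no bearing on the primary test or the sample size.

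**What to change.** Add to Section 11.7.2, or to the statistical analysis plan before unblinding:

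- For the SOFA day count, estimate the arm difference with a 95% confidence interval adjusted for baseline SOFA score.
- For the vasopressor-free day count, do the same adjusted for vasopressor use at screening (yes or no).
- Name the model, for example a linear model with robust standard errors, since the counts are bounded and many subjects may die.
- Keep the unadjusted summaries by arm alongside.

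Tables by starting state within arm are optional: at a 50% share each cell would hold only about 12 subjects, so they would be hard to interpret.

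The cost is a few lines of text and one extra model term per endpoint. No new data, visits or patients are needed, and the primary analysis and clinical conduct are untouched. Naming the covariates now also avoids choosing them after an imbalance has been seen.

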### Rationale for GC4419 dosing plan:

- Extensive clinical experience in cancer patients supports the safety of 90 mg of GC4419 administered over 60 minutes for 35 doses (M-F, up to 7 weeks) concurrently with chemoradiotherapy.
- Cmax-related transient mild hypotension and orthostasis has been observed at the current 90 mg/60-minute infusion schedule, but this is less frequent with lower doses.
- Therefore, administering 90 mg of GC4419 IV over 180 minutes (3 hours) is expected to provide an additional margin of safety.
- The plasma half-life of GC4419 is approximately 2 hours.
- Pharmacokinetic results to date do not indicate significant plasma accumulation of GC4419 with repeated dosing.

- Results of GLP animal toxicology studies support a total daily dose of GC4419 up to 198 mg, administered for up to 14 days (compared with planned 7 days in the current study).
- Administration of a related dismutase mimetic to rats in the zymosan and *E. coli* sepsis models was performed over a period of several hours after challenge with zymosan or *E. coli*. Moreover, the persistent superoxide production is expected to be associated with the ongoing COVID-19 disease process. Accordingly, a dosing schedule that maintains extracellular concentrations of GC4419 as much as possible and feasible may be desirable.

In light of the above, subjects will receive, in a blinded fashion, either GC4419, 90 mg intravenously, or placebo, administered over 3 hours (180 minutes), repeated every 12 hours (+/- 2 hours) for 7 consecutive days.

Subjects requiring renal dialysis should not have that procedure performed at any time during GC4419/placebo infusion and until at least 2 hours after infusion. If continuous renal replacement therapy is required for >24 hours, dosing with blinded GC4419/placebo will be discontinued.

Adverse Events and Serious Adverse Events will be assessed daily during dosing of GC4419/placebo, then daily during hospitalization and weekly after hospital discharge, for a total of 30 days after the last dose of GC4419/placebo. Post-dosing AE assessment may be done on an outpatient basis for subjects who are discharged from the hospital.

Ongoing safety results will be monitored by an independent Data Monitoring Committee (DMC) that will operate under a specific DMC charter separate from this protocol document.

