### 6.2. Treatment Plan and Duration of Therapy

Subjects in the present trial will receive, in a blinded fashion, either GC4419, 90 mg intravenously, or placebo, administered over 3 hours (180 minutes), repeated every 12 hours (+/- 2 hours) for 7 consecutive days.

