## **9. TOXICITY MANAGEMENT**

### **9.1. Anticipated toxicities of GC4419**

Based on the drug's mechanism of action, adverse effects anticipated with GC4419 are attributable to transient potentiation of nitric oxide. Clinical results with GC4419 to date are consistent with this. These effects have been IV infusion related and transient, typically with onset during or at the end of infusion, resolving within 1-2 hours of cessation of GC4419 administration. At the dose and schedule planned in this trial, these effects may include mild hypotension, postural lightheadedness/presyncope, and perioral/facial tingling or paresthesia. Mild nausea and vomiting have also been observed in human subjects receiving GC4419.

See the investigator's brochure for additional details.

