### **9.2. Dose Delays and Dose Modifications for Toxicity**

*For any given subject, study drug infusions should not begin if the subject's mean arterial pressure (MAP) is less than 65 mmHg.*

For any given subject, hold blinded GC4419/placebo and reduce by 25% (from the initial dose) for all future infusions if:

- During infusion or within 1 hour of completing infusion, the subject experiences an acute decrease in systolic blood pressure requiring bolus fluid resuscitation OR requiring initiation of vasopressor therapy OR increased vasopressor therapy. Hold GC4419/placebo until the dose of vasopressor therapy is stable and bolus fluid resuscitation is not required.
- The subject develops serum creatinine  $> 5$  mg/dL. Hold GC4419/placebo until the creatinine is  $=< 5$  mg/dL.
- The subject develops serum total bilirubin  $> 6$  mg/dL, or AST or ALT  $> 10$  times upper limit of normal. Hold GC4419/placebo until the parameters in question are below these levels.
- The subject experiences a serious or severe adverse event considered by the investigator to be related or possibly related to blinded GC4419/placebo. Hold GC4419/placebo until the event is no longer serious or severe.

Up to two such dose reductions for a cumulative 50% from the initial dose of GC4419/placebo will be permitted for a given subject. If a subject cannot tolerate GC4419/placebo infusion after a 50% dose reduction, all dosing with GC4419/placebo for that subject will be discontinued.

Patients unable to tolerate GC4419/placebo must discontinue treatment with GC4419/placebo but should continue with other protocol assessments at the discretion of the treating investigator and with the ongoing consent of the subject.

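### Appendix 1, footnote 10 sets no minimum gap between doses 1 and 2, so a full dose 2 can start while dose 1's 1-hour hold-and-reduce window is still open

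*Combined protocol and SAP*

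**What the plan says.** The regular schedule, in Appendix 1, footnote 10, is "Administer 90 mg IV over 180 minutes, Q 12 hours (+/- 2 hours) for 7 days". Section 6.2 gives the same interval: "repeated every 12 hours (+/- 2 hours) for 7 consecutive days". Footnote 10 then adds "It is acceptable for the timing of the first 2 doses to be modified", so that later doses can follow the institution's 12-hourly routine. It gives neither a shortest nor a longest gap. Its next sentence bars starting an infusion when MAP is below 65 mmHg, a condition repeated in Sections 9.2 and 10.2.2.

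The Section 9.2 rule for falls in pressure applies when "During infusion or within 1 hour of completing infusion, the subject experiences an acute decrease in systolic blood pressure" and the fall needs a fluid bolus or new or increased vasopressor. The instruction is "Hold GC4419/placebo until the dose of vasopressor therapy is stable and bolus fluid resuscitation is not required", with all later infusions cut by 25% of the initial dose.

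Section 9.1 describes the expected infusion effects as "typically with onset during or at the end of infusion, resolving within 1-2 hours of cessation of GC4419 administration". Footnote 4 of Appendix 1 requires pressure readings "before each GC4419/placebo infusion, every 30 minutes during each GC4419/placebo infusion, at end of each GC4419/placebo infusion", and again 1, 2 and 4 hours afterwards.

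Sections 6.2 and 10.2.2 do not mention the exception for the first two doses, and Section 8.3.5 gives no gap. Section 4.2 mentions four hours between doses, but as a modelling result for a 60-minute infusion, not as a dosing rule.

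**The concern.** The drug's main acute toxicity is hypotension, and Section 9.2 is the rule that protects a subject who shows it. On the regular schedule the rule always has time to finish before the next dose. For the first two doses, footnote 10 removes the spacing that guarantees this and puts nothing in its place.

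Take a site with 09:00 and 21:00 slots and a subject first dosed at 18:00. Dose 1 ends at 21:00, and dose 2 may start at once. If pressure falls at 21:30, Section 9.2 would have had dose 2 held and then given at 67.5 mg (90 × 0.75). Instead, dose 2 is already running at the full rate. The hold still applies from that moment, but it can no longer delay dose 2 or lower the dose at which it started. This would happen at first exposure, in critically ill subjects, before their tolerance of the drug is known.

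**Working it through.** The plan gives no figure of its own to reproduce. The check is interval arithmetic, followed by a bound on exposure.

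**Inputs.** Infusion 3 h (Section 6.2), tolerance ± 6 min (Section 8.3.5); interval 12 ± 2 h (footnote 10); hold window to 1 h after the end of infusion (Section 9.2); 25 GC4419 subjects (Synopsis); Cmax 3650 ng/mL and AUC 7160 ng·h/mL for 90 mg in humans (Table 2).

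**1. When the window closes.** 3 + 1 = 4 h after dose 1 starts (4.1 h with the tolerance). On the regular schedule dose 2 comes no earlier than 12 − 2 = 10 h, which is 6 h after the window closes. Under the exception, a dose 2 starting 3 to 4 h after the start of dose 1 falls inside the open window.

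**2. Which falls are missed.**
- A fall during dose 1, or after it but before dose 2 starts: seen at the end-of-infusion or pre-infusion reading, and stopped by Section 9.2 or, if MAP is below 65 mmHg, by the start gate. Not missed.
- A fall after dose 2 starts and within 1 h of the end of dose 1: dose 2 is then held, but has already begun at full dose. This is the gap.

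**3. How much drug.** 90 mg / 3 h = 30 mg/h. The longest overlap is 1 h, at zero gap, so at most 30 mg of dose 2 is in when the fall begins.

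**4. How many subjects.** Assume fixed 12-hourly slots, evenly spread first-dose times, and dose 2 given at the next slot that does not overlap dose 1. Start times 3 to 4 h before a slot make up 1/12 of the total, and 25 × 1/12 = 2.1 subjects. If sites wait for the following slot, the number is 0.

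Within that group, if the gap and the onset of a late fall are each spread evenly over the hour, half of late falls come after dose 2 has begun. The documents give no rate of late falls. Assuming 10% to 50%:
- 2.08 × 0.5 × 0.10 = 0.10
- 2.08 × 0.5 × 0.50 = 0.52

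**5. Exposure.** Section 4.2 calls plasma exposure approximately dose-proportional. Clearance is then dose/AUC, and a 30 mg/h infusion run indefinitely cannot exceed 30 × 7160 / 90 = 2387 ng/mL. Against the Table 2 peak, 2387 / 3650 = 0.65. This takes the Table 2 dose to be a 60-minute infusion. Back-to-back 3-hour infusions therefore stay at or below 0.65 of that peak.

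**The case against.** The best defence is that the protocol already covers nearly all of the risk. The exception is permissive and has a stated scheduling purpose. A site could equally lengthen the gap, and Sections 6.2 and 10.2.2 read alone would still require at least 10 hours. Typical onset is during or at the end of infusion, so most reactions to dose 1 would be visible before dose 2. The MAP gate applies to every infusion and was added on the DMC's recommendation. The separate Pharmacy Manual, which is not in the documents, might set a floor. Delaying dose 2 also has a price, since the dosing rationale in Section 6.2 says "a dosing schedule that maintains extracellular concentrations of GC4419 as much as possible and feasible may be desirable".

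Most of this stands, and it is why the point is small. It does not remove the gap: one reading before dose 2 cannot detect a fall that has not yet begun.

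Two stronger readings are tempting, and the documents do not support either. A reader might infer that no fall after the end of dose 1 can stop dose 2. That is true only at zero gap; otherwise, any fall before dose 2 starts is caught. A reader might also infer overexposure, because a one-compartment model with the stated 2-hour half-life puts the second of two back-to-back peaks at about 1.00 times the 60-minute peak. That model does not fit the protocol's data. It predicts a 60-minute peak of 7160 × (1 − e^(−ln2/2)) = 2097 ng/mL, 43% below the reported 3650, and Section 4.2 describes the decline as bi-exponential. The Table 2 bound is the better guide.

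**Conclusion.** The point holds, as a minor one. Footnote 10 lets dose 2 start at full dose within 1 hour of the end of dose 1, so one dosing instruction can overtake a stated safety rule. The loss is confined to falls that begin after dose 2 starts and inside dose 1's last hour of cover. Monitoring continues, and the hold still operates once such a fall is seen.

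The subject counts rest on the slot pattern and on an assumed late-fall rate, and would be zero at sites that wait. The exposure bound rests on dose-proportionality and on a 60-minute infusion in Table 2. What is missing is a safety floor at first exposure. The primary analysis is not touched.

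**What to change.** Add to footnote 10 and to Sections 6.2 and 10.2.2:

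*Dose 2 must start no sooner than 2 hours after the end of dose 1, and only if MAP is at least 65 mmHg and no Section 9.2 hold criterion is active. If one was met, Section 9.2 governs restart and the 25% reduction. If the site's slot falls sooner, start dose 2 up to 2 hours after the slot; dose 3 then follows at the regular slot, at least 10 hours later.*

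One hour is the least that closes the Section 9.2 window. Two hours also covers the 1-to-2-hour resolution time in Section 9.1 and the 1- and 2-hour pressure checks in footnote 4. In the example above, dose 2 moves from 21:00 to 23:00, and dose 3 at 09:00 is 10 hours later, inside the ± 2 hour window.

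The cost is that dose 2 moves by up to 2 hours for the 2/12 of start times that lie 3 to 5 hours before a slot (about 25 × 2/12 = 4 GC4419 subjects), and sites lose a little scheduling freedom. No 12-hour delay is needed for these subjects, and later doses do not change. Where the slot comes less than 3 hours after dose 1 starts, dose 1 is still running at the slot time; dose 2 goes to the following slot, as the slot assumption already has it.

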### **11.3. Randomization and Stratification**

Eligible subjects will be randomized 1:1 to the two treatment arms using a permuted block randomization schedule. Randomization will be stratified by age (<60 versus  $\geq$ 60 years).

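### Cytokines and viral load at Days 7 and 14 are sampled only in subjects alive and in hospital, which can mask a true fall on GC4419, most of all at Day 14

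*Combined protocol and SAP*

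**What the plan says.** Section 5.3 makes cytokines (IL-6, TNF-alpha, IL-1 beta, IL-10) and viral load exploratory objectives. For cytokines it asks for levels before, during and after treatment.

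Appendix 1 sets the sampling. Footnote 11, on cytokines: "Collected once during screening/baseline, at Day 7 and Day 14 (while in the hospital". Footnote 13, on viral load: "Subsequent samples collected at Day 7 and Day 14 (while in the hospital) for central lab analysis". Footnote 13 also lets the specimen depend on the subject's state: "Nasopharyngeal sample required unless subject is intubated, in which case pulmonary secretion collected". Footnote 18 lets a visit be virtual or by phone when the subject cannot attend, and such a contact yields no specimen.

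The analysis is one sentence in Section 11.7.2: "Secondary and exploratory endpoints will be analyzed descriptively, and results tabulated". It adds percentages and 95% intervals where appropriate. Section 11.1 defers technical detail to a separate SAP. Nothing in the available text says how death or discharge before a sample is handled.

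**The concern.** A Day 14 table by arm would condition on two events after randomisation that the drug is meant to change. Survival is the primary endpoint, and ICU-free and ventilator-free days are secondary. If sicker subjects carry higher values, the two exits add rather than cancel: deaths take high values out of the control sample, and earlier discharge takes low values out of the GC4419 sample. The GC4419 values then look higher than they should.

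The direction matters differently by marker. Section 4.1.3 expects TNF-alpha, IL-1 beta and IL-6 to fall, so an upward shift hides benefit. It expects IL-10 to rise, so the same shift would flatter the drug. Day 14 is also the only scheduled sample after the 7-day course, so the after-treatment part of the objective rests on the most selected sample.

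Viral load has a second problem. A subject extubated between samples moves from pulmonary secretion to nasopharyngeal swab, so a change over time can be a change of specimen.

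**Working it through.** **Inputs from the documents.** Section 11.2: "the null hypothesis is that 50% of subjects will survive for 28 days", and the alternative is "at least 90% of subjects receiving GC4419 will survive for 28 days compared with the control survival of 50" percent. It adds: "25 in each group, is expected to provide approximately 80% power to detect this difference with a two-sided alpha of 0.05". Allocation is 1:1 (Section 11.3).

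**The plan's own figure.** For 50% v 90%, two-sided 0.05 and 80% power, the pooled normal formula gives 19.4 per arm. The continuity correction n/4 × [1 + √(1 + 4/(0.4n))]² raises this to 24.1, so 25 per arm, as stated. Fisher's exact test at 25 per arm has 83% power. The planning rates are used below as they stand.

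**Assumptions, not in the documents.** A constant hazard of death in each arm; correlation r of 0.3, 0.5 or 0.7 between the log marker and the severity that decides death; no true drug effect on the marker.

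**Deaths before each sample.** Proportion dead by day t = 1 − S^(t/28), where S is 28-day survival.

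| | Control (S = 0.5) | GC4419 (S = 0.9) |
|---|---|---|
| Dead by Day 7 | 15.9% (4.0 of 25) | 2.6% (0.6 of 25) |
| Dead by Day 14 | 29.3% (7.3 of 25) | 5.1% (1.3 of 25) |

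**Shift from deaths alone.** If the sickest fraction q dies, the mean severity of those left is −φ(z)/(1 − q), where z cuts off the upper tail q.

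- Day 14: control −0.344/0.707 = −0.486; GC4419 −0.105/0.949 = −0.111; difference 0.375. Times r: **0.11, 0.19, 0.26 SD** of the marker, upward on GC4419.
- Day 7: control −0.242/0.841 = −0.288; GC4419 −0.060/0.974 = −0.062; difference 0.226. Times r: **0.07, 0.11, 0.16 SD**.

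**Against noise.** At Day 14, 25 − 7.3 = 17.7 and 25 − 1.3 = 23.7 subjects remain. SE = √(1/17.7 + 1/23.7) = 0.31 SD, and the 95% half-width is 1.96 × 0.314 = 0.62 SD. The death-only shift is below one SE.

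**Adding discharge.** If 10% of control and 30% of GC4419 subjects (assumed, the least sick) have gone home by Day 14, the difference in mean severity becomes 0.65 and the shift is 0.20, 0.33, 0.46 SD. With 15.2 v 16.2 subjects left, the SE is 0.36, so only r = 0.7 exceeds one SE.

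Dropping the constant hazard, and letting 50% to 90% of 28-day deaths fall by Day 14 with discharge from 0%/0% to 20%/40%, gives +0.09 to +0.56 SD. The shift is upward in every case.

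**If the drug does lower the marker.** Suppose all benefit runs through lower severity, with the same thresholds for death and discharge, 70% of deaths by Day 14 and 10% control discharge. A true shift of −1.09 severity SD is then seen as −0.23. About 79% is lost (1 − 0.23/1.09), but the sign is kept. The sign was kept in every such scenario run. If part of the benefit bypasses the marker, the sign flips only when the true lowering is below about 0.57 to 0.69 severity SD (70% of deaths by Day 14; discharge from 5%/15% to 20%/40%).

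**The case against.** Five points deserve an answer.

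1. **A reader might infer that a drug working as hypothesised would appear to raise these markers.** The documents do not support that. The hypothesis in Section 4.1.3 includes lower TNF-alpha, IL-1 beta and IL-6, whereas the shifts above assume no marker effect. Selection mainly masks a fall. Reversal needs the true fall to be small or the benefit to bypass the marker.
2. **A reader might infer that the mechanism has no other test.** It has: the mean arterial pressure, vasopressor and oxygenation endpoints (Section 11.5.2) and lung compliance (Section 11.5.3) bear on it. Viral load is a weak mechanism marker, since Section 4.1.3 reports very little testing of the class in viral models.
3. **The bias is small against the noise.** True for deaths alone. Discharge could make it larger, but the documents give no discharge rates, and the Synopsis says intensive care often lasts 14 days or more, which limits early discharge.
4. **Day 7 has the same in-hospital condition.** True. It carries about 60% of the Day 14 death-only shift (0.226/0.375), so it is less affected but not clean.
5. **The endpoints are exploratory in a 50-subject pilot, and hospital-only sampling is a matter of feasibility.** Also true. No test or stopping rule uses these markers, and samples lost to death cannot be recovered. That limits the severity, but does not justify leaving Day 14 values unexplained.

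**Conclusion.** The concern holds as a low-severity analysis point. Day 7 and Day 14 values describe survivors still in hospital, and a comparison by arm is shifted upward on GC4419 if the drug saves lives or speeds discharge and sicker subjects have higher values. Deaths alone give about 0.11 to 0.26 SD at Day 14 and 0.07 to 0.16 SD at Day 7; discharge would add to this. The consequence is a masked fall in the pro-inflammatory cytokines or viral load, possible reversal of a small fall, and possible flattery for IL-10.

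The direction rests on the assumed link between severity and the marker. The size also rests on assumed death timing, discharge and correlation. Only the survival rates, the sample size and the sampling rule come from the documents. Detail in the separate SAP could already cover this, but none is in the available text.

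**What to change.** In Section 11.7.2 or the SAP:

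1. Make the main between-arm cytokine contrast the Day 7 log value, adjusted for the baseline log value and age stratum, with a 95% interval. State that Day 7 is less affected by the selection but not free of it.
2. At both Day 7 and Day 14, show for each arm the number dead, discharged alive, in hospital but unsampled, and sampled. Label Day 14 values as describing those still in hospital, not as a treatment effect.
3. Report viral load by specimen type, nasopharyngeal or pulmonary. Note also that footnote 14 lets the baseline test be up to 7 days old.

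I would not add a Day 14 rank summary with death as the worst rank. With 7.3 v 1.3 expected deaths it would largely restate mortality. It also gives no place to subjects discharged alive, and it has no obvious direction for IL-10.

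The cost is wording and a few lines of code, with no new samples or visits. Adjustment should also gain precision. With deaths only, 21.0 v 24.4 subjects remain at Day 7, and the unadjusted 95% half-width is 1.96 × √(1/21.0 + 1/24.4) = 0.58 SD. An assumed baseline correlation ρ of 0.5 to 0.7 cuts the variance by ρ², or 25% to 49%, and the half-width to 0.58 × √(1 − ρ²), about 0.51 to 0.42 SD.
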